16.1.4. TEAEs AND POST-TREATMENT AEs LEADING TO DISCONTINUATION OF STUDY

TEAEs and post-treatment AEs leading to study discontinuation will be identified as an AE for which the question “Did the AE cause the subject to discontinue from the study?” is reported as “Yes” on the Adverse Events eCRF. A summary of TEAEs leading to study discontinuation by SOC and PT will be prepared. If a subject reports a TEAE leading to study discontinuation more than once within that SOC/PT, the subject will be counted only once for that SOC/PT.

Additionally, a listing of all AEs leading to study discontinuation will be provided.

16.1.5. ADVERSE EVENTS LEADING TO DEATH

TEAEs and post-treatment AEs leading to death are those events for which “Outcome” is reported as “Death” on the Adverse Events eCRF, or the seriousness criteria is indicated as “Death”. A summary of TEAEs and post-treatment AEs leading to death by SOC and PT will be prepared.

Additionally, a listing of all AEs leading to death will be provided.

16.2. LABORATORY EVALUATIONS

Results from the local and central laboratories will be included in the reporting for this study.

- Local Laboratories:
 - Hematology
 - Chemistry
 - Serum cortisol levels at screening
- Central laboratories:

- Morning Serum cortisol after screening

The local laboratory results will be converted to standard units by data management and transferred to biostatistics for use in the analysis.

Quantitative laboratory measurements reported as “< X”, that is below the lower limit of quantification, or “> X”, that is above the upper limit of quantification, will be converted to X for quantitative summaries.

The following summaries will be provided for laboratory data:

- Observed values and change from baseline by visit for quantitative measurements.
- Shift from baseline according to investigator assessment (abnormal CS, abnormal NCS, or normal as indicated by the investigator on the Hematology, Blood Chemistry, and Adverse Events eCRFs).

Since the results are originating from various local laboratories, a single set of reference ranges is not available for use in the analysis. Prior to summarizing, the lab results will be normalized as described in Section 16.2.1.

The laboratory tests to be presented in the analysis tables are listed in the protocol Sections 8.4.3.1 to 3. Any other lab test will be listed only.

16.2.1. LABORATORY STANDARDIZATION

As the results are from local laboratories, laboratory parameters will have different normal ranges in the database. Prior to the analysis, observed values of all subjects will be standardized to a unique set of normal range using the location-scale standardization formula (Chuang-Stein, 1992):

$$s = LS + (x - LX) \frac{US - LS}{UX - LX}$$

where:

s = standardized observed value;

x = original observed value;

LS = Lower Limit of the normal range chosen to be the standard normal range;

US = Upper Limit of the normal range chosen to be the standard normal range;

LX = Lower Limit of the normal range associated with the original observed value;

UX = Upper Limit of the normal range associated with the original observed value;

It is to be noted that the choice of the standard normal range is arbitrary for all laboratory parameters except serum cortisol. Serum cortisol is collected by both central and local laboratories and for analysis purposes the central laboratory ranges will be used as the standard normal range.

16.2.2. PREGNANCIES

A serum pregnancy test will be conducted on females of child bearing potential at screening and prior to randomization on day 1. Urine pregnancy tests will be conducted thereafter at the time points specified in the schedule of assessments in Section 8.1 of the protocol. These data will be listed only.

16.3. VITAL SIGNS

The following vital signs measurements will be reported for this study:

- Systolic Blood Pressure (mmHg)
- Diastolic Blood Pressure (mmHg)
- Pulse Rate (bpm)
- Respiration Rate (breaths/min)
- Weight (kg)
- Body Mass Index (kg/m²)
- Temperature (°C) (to be listed only)

The following summaries will be provided for vital signs data:

- Observed, change from baseline by visit for quantitative measurements
- Incidence of abnormal values according to investigator criteria
- Shift from baseline according to investigator assessment (abnormal CS, abnormal NCS, or normal as indicated by the investigator on the eCRF).

16.4. PHYSICAL EXAMINATION

A physical examination will be conducted at Screening, Day 1, and Weeks 4, 12, 24, 28 and 48. This will consist of an assessment of all body systems including the skin, eyes, ears, nose and throat. These data will be listed only.

16.5. OTHER SAFETY ASSESSMENTS

16.5.1. OPHTHALMOLOGY ASSESSMENT

Ophthalmologic assessments will be performed at the site and result reported on the Ophthalmology Examination eCRF.

- Intraocular pressure (IOP) results will be summarized as follows:
 - Observed values and change from baseline in IOP by visit
 - Incidence of elevated IOP in one or both eyes
 - Clinically significant increase of IOP in one or both eyes
 - Shift from baseline according to investigator assessment (abnormal or normal as indicated by the investigator on the eCRF)
- In addition, the slit-lamp examination results will be reported in a descriptive summary table.
 - The summary will include the number and percentage of subjects with newly identified or worsened cataracts in one or both eyes as assessed per the protocol schedule of events.
 - A further classification between abnormal not affecting vision and abnormal affecting vision will also be presented.
 - For subjects with different results for left and right eyes, the worst-case result will be reported for the relevant visit, that is abnormal affecting vision.

16.5.2. OPHTHALMOLOGY SPECIFIC DERIVATIONS

- Elevated IOP is defined as results > 21 mmHg in one or both eyes.
- A clinically significant increase of IOP is defined as IOP in one or both eyes > 28 mmHg or an increase of IOP from Baseline in one or both eyes ≥ 10 mmHg.
- Newly identified or worsened cataracts will be identified as follows:
 - Mature or Morgagnian cataract present reported as “Yes”

- Nuclear cataract reported at a higher grade than the Screening result
- Cortical cataract reported at a higher grade than the Screening result
- Central Optical zone involvement reported as “Yes”
- Posterior subcapsular cataract reported at a higher grade than the Screening result.

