
To evaluate the safety and tolerability of LYR-210
	
 
- Severity and percentage of subjects reporting treatment-emergent adverse events (TEAEs) and serious adverse events (TESAEs) through Weeks 2, 4, 12, and 24
 
- Severity and percentage of subjects reporting Day 1 administration procedure and Week 24 removal procedure related AEs and SAEs
 
- Severity and percentage of subjects reporting product related AEs and SAEs on Day 1 and through Weeks 2, 4, 12, and 24
 
- Percentage of subjects with clinically significant abnormal and clinically significant abnormal laboratory values (hematology and chemistry, vital signs) on Day 1 and at Weeks 4, 12, and 24
 
- Morning serum cortisol levels on Day 1 and at Weeks 4, 12, and 24
 
- Severity and percentage of subjects with adverse nasal endoscopic findings and adverse nasal endoscopic findings requiring medical treatment in one or both nostrils on Day 1 and at Weeks 2, 4, 12, and 24
 
- Percentage of subjects with elevated intraocular pressure (IOP) in one or both eyes at Weeks 4, 12, and 24
 
- Percentage of subjects with a clinically significant increase of IOP at Weeks 4, 12, and 24
 
 
A clinically significant increase of IOP is defined as IOP in one or both eyes > 28 mmHg or an increase of IOP from Baseline in one or both eyes <math>\geq</math> 10 mmHg.
 
 
- Percentage of subjects with newly identified or worsened cataract in one or both eyes by slit-lamp examination at Week 24
 

To evaluate the time to onset of action of LYR-210
	
 
- Time to onset of action
 
 
Time to onset of action is defined as, within the first 30 days, the time when all subsequent mean CFBL in the CS7DA4S score of the LYR-210 is statistically significantly greater than that for the sham procedure.

To evaluate the efficacy of LYR-210 in improving CS7DA4S score and the 7-day average score of each of the 4 cardinal CS symptoms
	
 
- CFBL in the CS7DA4S score at Weeks 8, 12, 16, and 20
 
- CFBL in 7-day average score of nasal blockage/obstruction/congestion, reduction/loss of sense of smell, facial pain/pressure, and anterior/posterior nasal discharge at Weeks 1, 2, 3, 4, 8, 12, 16, 20, and 24
 

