  13. Has had more than 1 episode of epistaxis with frank bleeding requiring medical attention within 2 months of Screening visit or more than 1 episode of epistaxis with frank bleeding within 1 month of Screening visit.
  14. Has had acute exacerbation of nasal allergy or chronic sinusitis, upper respiratory tract infection (URTI), or common cold within 4 weeks of the Screening visit.
  15. Had dental procedure/implant on maxillary dentition within 4 weeks of the Screening visit.
  16. Has past or present acute or chronic intracranial or orbital complications of CS (e.g., brain abscess, related problems with eyes or central nervous system).
  17. History or diagnosis (in either eye) of glaucoma or ocular hypertension (IOP > 21 mmHg).
  18. With prior cataract surgery or presence (in either eye) of posterior subcapsular cataract of grade 2 or higher, nuclear sclerosis of grade 3 or higher, or cortical cataract of grade 2 or higher or involving a minimum of center optic zone of 3 mm diameter.
  19. Past or present functional vision in only one eye.
  20. Diagnosed with ongoing rhinitis medicamentosa.
  21. Known history of immune dysfunction including immune deficiency (IgG subclass deficiency or IgA deficiency) or autoimmune disease (e.g., Wegener's granulomatosis, sarcoidosis).
  22. Past, present, or planned organ transplant or chemotherapy with immunosuppression.
  23. History or diagnosis of ciliary dysfunction (e.g., cystic fibrosis, primary ciliary dyskinesia [Kartagener syndrome]).
  24. Past or present systemic vasculitis (e.g., granulomatosis with polyangiitis).

25. Evidence of disease or condition expected to compromise survival or ability to complete follow-up assessments.
26. Pregnant or breast feeding. Females of child-bearing potential must test negative for pregnancy at the time of screening based on a serum pregnancy test and reverified at the time of enrollment based on a urine pregnancy test. Both male and female subjects of reproductive potential must agree to use highly effective methods of birth control, throughout the study.
27. Previously participated in LYR-210 Phase I clinical study or received an experimental treatment in another clinical study within 5 half-lives of Screening visit.
28. Currently participating in an investigational drug or device study.

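### Two of the five SAP criteria for new or worsened cataract count a post-treatment finding without comparing it with Screening

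*SAP*

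**What the plan says.** Protocol section 3 lists as a safety endpoint the "Percentage of subjects with newly identified or worsened cataract in one or both eyes by slit-lamp examination at Week 24", and repeats it at Week 48 among the exploratory endpoints. Protocol 10.5 says that slit-lamp abnormalities will be summarized by visit as treatment-emergent incidence.

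SAP 16.5.2 gives the derivation. Three of its items are comparisons:

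- "Nuclear cataract reported at a higher grade than the Screening result"
- "Cortical cataract reported at a higher grade than the Screening result"
- "Posterior subcapsular cataract reported at a higher grade than the Screening result"

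The other two are not:

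- "Mature or Morgagnian cataract present reported as" 'Yes'
- "Central Optical zone involvement reported as" 'Yes'

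SAP 16.5.1 adds no baseline condition for these two. It specifies a shift-from-baseline summary for intraocular pressure but none for the slit-lamp examination. SAP 3.3, which lists departures from the protocol's analyses, does not mention the cataract derivation.

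On entry, exclusion 18 in protocol 5.4 applies to either eye. It sets grade limits for posterior subcapsular cataract (excluded from grade 2 upward) and for nuclear sclerosis (excluded from grade 3 upward). Its third limit concerns cortical change and excludes "cortical cataract of grade 2 or higher or involving a minimum of center optic zone of 3 mm diameter". It also bars prior cataract surgery.

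**The concern.** The endpoint is a change since Screening, but two of its five routes test presence only. A subject with 'Yes' on either item at Screening and the same 'Yes' at Week 24 has neither a new nor a worsened cataract, yet meets the definition. If nothing changes later, the same subject meets it again at Week 48.

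What is at stake is the accuracy of the cataract count in a study of a 24-week corticosteroid depot at two doses. Few events are likely, so one or two prevalent findings counted as incident would be a visible share of the total. The slit-lamp summary as specified would not let a reader separate the two kinds of finding.

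**Working it through.** The documents state no cataract rate, so there is no figure to reproduce. The check is of the rule's logic, followed by the weight of one subject.

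**1. The five items applied to an eye with identical findings at Screening and Week 24**

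| Item in SAP 16.5.2 | Compared with Screening? | Can an unchanged eye be counted? |
|---|---|---|
| Nuclear grade | Yes | No |
| Cortical grade | Yes | No |
| Posterior subcapsular grade | Yes | No |
| Mature or Morgagnian cataract | No | Yes, if present at Screening |
| Central optical zone involvement | No | Yes, if present at Screening |

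**2. What exclusion 18 leaves.** Grades 0 to 3 are an assumed range. The size limit in exclusion 18 is read as barring central involvement of 3 mm or more. Eligible grades are then nuclear 0 to 2, cortical 0 to 1 and posterior subcapsular 0 to 1: 3 × 2 × 2 = 12 combinations. Among eligible unchanged eyes, the rule as written still counts:

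- 12 patterns with central involvement below 3 mm only;
- 12 with mature or Morgagnian cataract only;
- 12 with both.

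That makes 36 patterns. With a Screening comparison added to the two items, 0 of the 36 are counted. These are logical patterns, not frequencies. Some may be clinically implausible, and they say nothing about how many subjects would show them.

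**3. Routes by which a 'Yes' at Screening could reach the count**

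- *Central involvement below 3 mm.* The SAP item has no size limit, while exclusion 18 mentions 3 mm. This route is open only if the eCRF records smaller involvement as 'Yes'. The eCRF threshold is not in the documents.
- *Mature or Morgagnian cataract.* Exclusion 18 does not name it. The graded limits, and exclusion 19 (functional vision in only one eye), make it remote.
- *Ineligible subjects who were treated.* SAP 16 bases safety outputs on the SAF, which under SAP 5.4 takes every treated or attempted subject without an eligibility condition. Protocol 11.6 names enrollment of an ineligible subject as an example of a deviation.

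**4. Weight of one subject**

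- Arm size: 70 / 3 = 23.3. From the sample size section, (63 + 6) / 3 = 23 and (63 + 9) / 3 = 24.
- One subject: 1/23 = 4.3% and 1/24 = 4.2%.
- Two subjects in one arm: 2/23 = 8.7% and 2/24 = 8.3%.

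This is the weight of any single subject in any count. It does not estimate the size of the error, because the number affected is unknown.

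**The case against.** The strongest reply is that entry criteria already do the work of the missing comparison. The wording of exclusion 18 is awkward: the 3 mm may describe the central zone itself rather than set a minimum size. On that reading any cortical involvement of the zone is excluded. SAP 16.5.2 places central zone involvement directly after cortical grade, the same pairing as in exclusion 18, which suggests that both refer to one eCRF item. A post-treatment 'Yes' in an eligible subject would then be new by design. In addition, the intent is clear from the endpoint and from protocol 10.5, the examiner is blinded (protocol 8.4.5), and the protocol synopsis promises subject listings in which a prevalent 'Yes' could be seen.

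Much of this stands. A 'Yes' at Screening should be rare, and on the narrower reading the sub-3 mm route closes for eligible subjects. It does not remove the other two routes, and neither document says which reading applies. A listing helps a careful reader but does not correct the tabulated percentage.

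A reader might go further and infer that pre-existing findings will be reported as an ocular effect of the steroid, or that the rule creates or hides a dose signal. The documents do not support that. The count is made in all arms including sham, protocol 10.5 rules out formal tests on safety endpoints, and neither document attributes this count to the drug.

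**Conclusion.** The inconsistency is real and the point is minor. Two of five criteria do not measure the change that the endpoint names, and the entry criteria reduce the consequence without eliminating it. Any affected subject would be counted as new or worsened at Week 24 and Week 48 with no change, at roughly 4 percentage points per subject in an arm of about 23 to 24.

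This rests on three things that the documents leave open: the eCRF threshold for a 'Yes' on central zone involvement, the meaning of 3 mm in exclusion 18, and whether any ineligible subject with such a finding was treated. It would be too strong to say that unchanged findings *are* being miscounted. The plan allows it, and the actual number may be zero.

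**What to change.** In SAP 16.5.2, change both presence-only criteria so that they count only when the item is 'Yes' in an eye for which it was 'No' at Screening. State that each eye is compared with its own Screening result on all five items before combining to one or both eyes. The SAP does not say this now, and the worst-case rule for differing eyes in SAP 16.5.1 could be misread as collapsing the eyes first.

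The cost is a sentence in the SAP and a condition in the program. The slit-lamp examination is already scheduled at Screening, Week 24/EOT and Week 48/EOS (protocol 8.4.5), so no new data are needed. A truly new finding in an eye recorded as 'No' at Screening would still be counted.

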16.6. NASAL ENDOSCOPY ASSESSMENT

Nasal cavities will be assessed by endoscopy procedure as per the schedule of events in Section 8.1 of the protocol. The severity and percentage of subjects with adverse nasal endoscopic findings in one or both nostrils will be summarized by visit and by treatment group.

17. PHARMACOKINETIC ANALYSES

The PK analyses will be performed based on subjects in the PK analysis set with available data by treatment group as follows:

- Concentrations, nominal times post-dose, and actual times will be listed.
 - In listings, concentrations below the lower limit of quantification (LLOQ) will be reported as “<LLOQ”, where LLOQ will be the actual value of LLOQ.
- A separate listing will present deviations from the nominal times per protocol.
- Descriptive statistics will be presented for concentrations by dose and nominal time post-dose including number (n), mean, SE, standard deviation, coefficient of variation (CV), median, minimum, maximum, geometric mean, geometric CV%, and the number of concentrations greater than or equal to LLOQ.
 - The “<LLOQ” values will be set to zero based on the Beal’s method M7 (Beal, 2001).

APPENDIX 1. PROGRAMMING CONVENTIONS FOR OUTPUTS

PAPER SIZE, ORIENTATION AND MARGINS

The size of paper will be Letter, and the page orientation will be landscape. Margins will provide 1 inch (2.54 cm) of white space all around the page.

DATES AND TIMES

Depending on data available, dates and times will take the form DDMMYYYY HH:MM.

SPELLING FORMAT

United States English.

PRESENTATION OF TREATMENT GROUPS

For outputs, treatment groups will be represented as follows and in the given order:

- LYR-210 2500µg
- LYR-210 7500µg
- Sham

PRESENTATION OF VISITS

For tables and figures, visits will be represented as follows and in that order:

Long Name (default)	Short Name
Screening	Scr
Baseline	BL
Week 2	WK 2
Week 4	WK 4
Week 8	WK 8
Week 12	WK 12
Week 16	WK 16
Week 20	WK 20
Week 24	WK 24

Long Name (default)	Short Name
Week 28	WK 28
Week 32	WK 32
Week 36	WK 36
Week 40	WK 40
Week 44	WK 44
Week 48	WK 48

For Listings the visit will be presented as derived in Section 6.6.

LISTINGS

All listings will be ordered by the following (unless otherwise indicated in the template):

- Randomized treatment group (or treatment received if it's a safety output) in order of LYR-210 2500 µg, LYR-210 7500 µg and Sham procedure.
 - For listings where non-randomized subjects are included, these will appear in a category after the randomized treatment groups labeled “Randomized, Not Treated” and “Screen Failure”.
- Subject ID
- Parameter (where applicable)
- Date (where applicable)

GENERAL CONVENTIONS

- Decimal precision:
 - If the original data has N decimal places, then the summary statistics should have the following decimal places:
 - Minimum and maximum: N
 - Mean and median: N + 1
 - SD: N + 2
 - Percentages will be presented to 1 decimal place
 - Zero count will not have percentage reported
 - Odd ratios will be presented to 2 decimal places
 - Ordering of footnotes:
-

Statistical Analysis Plan

- Abbreviations
- Definitions
- Formulae
- P-value significance footnote
- Symbols. They will appear in the same order as they are defined in the table or listing, from left to right.
- Specific notes
- Common notes from table to table should appear in the same order.

APPENDIX 2. PARTIAL DATE CONVENTIONS

ALGORITHM FOR TREATMENT EMERGENCE OF ADVERSE EVENTS

Start Date	Stop Date	Action
Known	Known/Partial/ Missing	If start date < insertion procedure, then Prior If insertion procedure <= start date <= removal procedure + 28 days , then TEAE If start date > removal procedure + 28 days, then Post-Treatment AE
Partial, but known components show that AE started before insertion procedure	Known/Partial/ Missing	Assumed Prior
Partial, known components show that AE started on/after insertion procedure but before/on removal procedure + 28 days OR Missing	Known/Partial/ Missing	Assumed TEAE
Partial, known components show that AE started after removal procedure + 28 days	Known/Partial/ Missing	Assumed Post-Treatment AE

ALGORITHM FOR PRIOR/CONCOMITANT MEDICATIONS

Start Date	Stop Date	Action
Known	Known	If stop date < insertion procedure, assign as Prior If stop date >= insertion procedure and start date <= removal procedure+28 days, assign as Concomitant If start date > removal procedure+28 days, assign as Post-Treatment.

Start Date	Stop Date	Action
	Partial	If known date parts of stop date < insertion procedure, assign as Prior If known date parts of stop date >= insertion procedure and start date <= removal procedure+28 days, assign as Concomitant If start date > removal procedure+28 days, assign as Post-Treatment
	Missing	If stop date is missing could never be assumed a Prior medication If start date <= removal procedure+28 days, assign as Concomitant If start date > removal procedure+28 days, assign as Post-Treatment
Partial	Known	If stop date < insertion procedure, assign as Prior If stop date >= insertion procedure and known date parts of start date <= removal procedure+28 days, assign as Concomitant If known date parts of start date > removal procedure+28 days, assign as Post-Treatment
	Partial	If known date parts of stop date < insertion procedure, assign as Prior If known date parts of stop date >= insertion procedure and known date parts start date <= removal procedure+28 days assign as Concomitant If known date parts of start date > removal procedure+28 days, assign as Post-Treatment
	Missing	If stop date is missing could never be assumed a Prior medication If known date parts of start date <= removal procedure+28 days, assign as Concomitant If known date parts of start date > removal procedure+28 days, assign as Post-Treatment
Missing	Known	If stop date < insertion procedure, assign as Prior If stop date >= insertion procedure, assign as Concomitant Cannot be assigned as Post-Treatment
	Partial	If known date parts of stop date < removal procedure+28 days, assign as Prior If known date parts of stop date >= removal procedure+28 days, assign as Concomitant Cannot be assigned as 'Post-Treatment'
	Missing	Assign as Concomitant

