**Figure 1: Study Design Schematic**

#### **4.1.1 Screening Stage**

After providing written informed consent, subjects who are qualified to participate in this study will have an initial Screening visit. Immediately following the initial Screening visit, subjects will undergo a minimum of 2-week but a maximum of 4-week washout period. During this washout period, subjects will receive no active treatment for CS but are recommended to start daily saline irrigation twice a day. Subjects will be provided with saline and instructions for daily intranasal saline irrigations while participating in the study.

Medications that are prohibited during the washout period (and during the study) are listed in Section 6.4.2. Beginning at least 7 days prior to Day 1 visit, subjects will record the severity of the 4 cardinal symptoms of CS and the use of saline irrigation each day in the morning on the electronic subject reported outcomes (ePRO) questionnaire.

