#### **8.4.9.6 Reporting**

##### **8.4.9.6.1 Adverse Event Reporting**

Adverse events are to be collected from the time a subject signs informed consent until the completion of all follow-up visits. At each office visit during the study, AEs that have occurred since the previous office visit must be recorded. All subjects will be evaluated for AEs or complications associated with the study procedure or the investigational product. The Investigator will determine the severity and relationship of each event, as defined above.

AEs observed during the course of this study, regardless of severity or relationship to the study procedure or investigational product will be recorded on the appropriate CRF.

Documentation of all new AEs or changes in previously reported AEs will be recorded. Pre-existing diseases or conditions will not be reported as AEs unless there has been a substantial increase in severity or frequency of the problem which cannot be attributed to the expected progression of the disease or condition.

The Investigator will review the results of all clinical and laboratory tests as they become available. For each laboratory test result, the Investigator will ascertain whether the result represents an abnormal (e.g., clinically significant) change from Baseline for that individual subject. If this laboratory test result is determined to be an abnormal change from Baseline for that subject, the value will be considered to be an AE.

The description of the AE will include the date of onset, date of resolution (ongoing), severity, seriousness, relationship of the event to the investigational product and to the study procedure, and any procedure required. Specific procedures implemented in response to the AE will also be recorded. For all AEs, the Investigator is required to supply any additional data that may be deemed necessary by the Sponsor or designee.

All AEs will be coded using the latest version of Medical Dictionary for Regulatory Activities (MedDRA) throughout the study (Version 21.1 will be used at the start of the study).

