16.1. ADVERSE EVENTS

AEs will be coded using MedDRA version 23.0 or later.

- Prior AEs are defined as any AE starting before the bilateral insertion/Sham procedure.
- Treatment emergent adverse events (TEAEs) are defined as any AE starting or worsening on or after the bilateral insertion/Sham procedure, but before or on 28 days after the removal/Sham procedure.
- Post-treatment AEs are defined as any AE starting or worsening more than 28 days after the removal/Sham procedure.

See [APPENDIX 2](#) for the handling of partial dates for AEs. In the case where it is not possible to define an AE as treatment emergent or not, the AE will be classified by the worst case (i.e. treatment emergent).

An overall summary of the number and percentage of subjects as well as the number of events within each of the categories below will be provided:

- TEAEs
- TEAEs by maximum severity
- TEAEs by highest relationship to study treatment
- TEAEs by highest relationship to study procedure
- Serious TEAE
- Serious TEAEs by maximum severity
- Serious TEAEs by highest relationship to study treatment
- Serious TEAEs by highest relationship to study procedure
- TEAE leading to treatment discontinuation
- TEAE leading to study discontinuation
- TEAE leading to death
- Post-treatment AEs
- Post-treatment AEs by maximum severity
- Post-treatment SAEs
- Post-treatment SAEs by maximum severity
- Post-treatment SAEs leading to study discontinuation
- Post-treatment SAEs leading to death.

Listings will include all AEs regardless of whether they are treatment emergent.

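### SAP Appendix 2 counts an adverse event with a wholly missing start date as treatment-emergent even when its stop date shows it ended before insertion

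*SAP*

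**What the plan says.** SAP Section 16.1 sets the definitions. "Prior AEs are defined as any AE starting before the bilateral insertion/Sham procedure". TEAEs are "defined as any AE starting or worsening on or after the bilateral insertion/Sham procedure", up to 28 days after removal. The section sends the reader to Appendix 2 for partial dates and adds a worst-case rule with a stated scope: "In the case where it is not possible to define an AE as treatment emergent or not", the event is taken as treatment-emergent.

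The adverse-event table in Appendix 2 has columns for start date, stop date and action. One row covers start dates that are "Partial, known components show that AE started on/after insertion procedure but before/on removal procedure + 28 days OR Missing". Its stop-date cell lists all three states (known, partial, missing) and its action is to assume a TEAE. The same three states fill the stop-date cell of every row, so the stop date never affects the result.

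The medication table in the same appendix works differently. For a missing start date with a known stop date it says: "If stop date < insertion procedure, assign as Prior".

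On the data side, Protocol Section 8.4.9.6.1 states: "Adverse events are to be collected from the time a subject signs informed consent until the completion of all follow-up visits". Protocol Section 4.1.1 puts "a minimum of 2-week but a maximum of 4-week washout period" between Screening and the procedure. Protocol Section 8.4.9.1 requires both the onset date and the end date of each event.

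**The concern.** The row merges two different situations. A partial start date whose known parts fall in the treatment window is evidence that the event is treatment-emergent. A wholly missing start date is evidence of nothing, and in that case the stop date is the only date left that can place the event. The table has a stop-date column but does not use it.

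Events are collected from consent, and two to four weeks of washout follow before any subject is treated. Events that begin and end before insertion can therefore be in the database. If such an event has a stop date but no start date, Appendix 2 puts it in the TEAE incidence and severity tables of the arm the subject later entered, although it was over before exposure. Those tables are the main display of tolerability in a three-arm trial of about 70 subjects, and they are read without formal tests, so the percentages themselves carry the message.

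**Working it through.** No power, alpha or sample-size figure depends on this point, and the plan states no figure to reproduce. The check is a comparison of the table with the definitions, followed by one line of arithmetic for scale.

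**Step 1: what the definitions imply.** Let *s* be the start date, *e* the stop date and *I* the insertion or sham date. An event cannot start after it stops, so *s* ≤ *e*. If *e* < *I*, then *s* < *I*, and the event is Prior under Section 16.1 whatever the exact value of *s*. Any worsening also happened no later than *e*, hence before *I*, so the worsening limb of the TEAE definition is not met either. A later recurrence would be a separate record, because Protocol Section 8.4.9.1 calls for a new form for each event.

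**Step 2: whether the worst-case rule covers it.** That rule applies only where emergence cannot be determined. By Step 1 it can be determined when *e* < *I*. The rule does not reach this case.

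**Step 3: every stop-date state for a missing start date.**

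| Stop date | Appendix 2 as written | SAP Section 16.1 | With the fix |
|---|---|---|---|
| Known, before insertion | TEAE | Prior | Prior |
| Partial, known parts before insertion | TEAE | Prior | Prior |
| Known, on or after insertion | TEAE | Undetermined, so TEAE | TEAE |
| Partial, cannot be placed against insertion | TEAE | Undetermined, so TEAE | TEAE |
| Missing | TEAE | Undetermined, so TEAE | TEAE |

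The table and the definition disagree in the first two rows only. The fix changes those two and nothing else.

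**Step 4: the medication table as comparator.** Its row for missing start and known stop tests the stop date against insertion, which is the test the adverse-event table lacks. The next medication row (missing start, partial stop) tests the stop date against removal plus 28 days. Read literally, that row would call a medication that stopped during treatment Prior, so it is not a model to copy.

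**Step 5: scale.** SAP Section 3.1 gives approximately 70 subjects randomized 1:1:1, so 70 / 3 = 23.3, or about 23 per arm. One misclassified subject adds at most 1 / 23 = 4.3 percentage points to that arm's incidence, overall or for one term. The addition is zero in any line of the table where the subject already has a genuine TEAE.

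**The case against.** The strongest reply is that this hardly ever happens and does little harm when it does. The event needs no start date at all, not even a year, because known parts that place the onset before insertion already send it to the Prior row. Yet it arose after consent, within a few weeks, and someone recorded when it ended. Onset date is a required item, and Protocol Sections 11.7 and 11.8 have missing data queried before lock. Washout precedes randomization, so there is no reason to expect such events to fall more in one arm than another. SAP Section 16.1 lists all adverse events whether or not they are treatment-emergent, so a reader could find any case. The error also over-counts harm, which many would call conservative.

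Most of that stands, and it keeps the point small. It does not make the rule right. Section 16.1 refers to Appendix 2 for date handling, so a programmer will code the table as printed. Over-counting is not reliably conservative either: a misplaced event in the sham arm narrows the apparent difference between active and sham.

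Three stronger readings are tempting, and the documents do not support them.

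- A reader might infer that a partial start date in the insertion month is also forced to TEAE when the stop date precedes insertion. It is not. That date matches no row of the table, so Section 16.1 governs, and its worst-case rule does not apply to an event that the stop date settles.
- A reader might infer that a misplaced event with no recorded relationship would also be set to related. SAP Section 16.1.1.2 limits that imputation to TEAEs starting on or after the procedure, a condition that an event ended before insertion does not meet. Being tabulated as a TEAE is also not attribution: relationship is a separate judgement by the investigator.
- A reader might infer a large distortion by supposing several affected subjects in one arm with the same term. Nothing in the documents supports a count; only the per-subject maximum can be stated.

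**Conclusion.** The point holds for one case: a wholly missing start date with a stop date, or known parts of one, before insertion. There Appendix 2 gives TEAE and the definitions in Section 16.1 give Prior, and the worst-case rule does not reconcile them.

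The size is at most about 4.3 percentage points of TEAE incidence per affected subject. This assumes about 23 treated subjects per arm and no other TEAE for that subject in the same line of the table. The number of affected subjects is unknown and probably small. Efficacy, power and alpha are untouched; only descriptive safety summaries change. This is a minor correction, worth making because the rule as written gives a wrong classification and the remedy is simple.

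**What to change.** Split the missing-start case off from its present row in the Appendix 2 adverse-event table and give it its own condition: if the stop date, or its known parts, falls before the insertion procedure, classify the event as Prior; otherwise assume TEAE as now. The worst-case treatment of every unresolved event is kept.

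As clarification only, the same test can be stated for partial start dates that cannot be placed relative to insertion, since the table is silent on them. Model the wording on the medication row for missing start and known stop, not on the row for missing start and partial stop, which compares with removal plus 28 days.

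The cost is one added line in the SAP and a check of the derivation program. It needs no new data and no protocol amendment.
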